## IWG 2003 AND ELN 2017 AML RESPONSE ASSESSMENT

AML Response Assessment	IWG 2003 AML Response Criteria 	ELN 2017 AML Response Criteria 	Issues Requiring Clarification(s)	Study-specific Modification(s): ASTX727-02
Complete Remission (CR)	
 
Morphologic leukemia-free state (MLFS) 
 
><5% blasts in an aspirate sample with marrow spicules and with a count of at least 200 nucleated cells. There should be no blasts with Auer rods.
 
> No residual evidence of extramedullary leukemia (such as CNS or soft tissue involvement).
 
> The presence of a unique phenotype (by flow cytometry) identical to what was found in the pretreatment specimen (eg, CD34, CD7 coexpression) should be viewed as persistence of leukemia.
 
 
 
Hemoglobin concentration or hematocrit has no bearing on remission status, although the patient must be independent of transfusions.
 
Absence of persistent blasts in the peripheral
 
	
 
Bone marrow blasts <5%
 
Absence of circulating blasts and blasts with Auer rods
 
Absence of extramedullary disease
 
ANC <math>\geq 1.0 \times 10^9/L</math> (1000/uL)
 
Platelet count <math>\geq 100 \times 10^9/L</math> (100,000/uL)
 
	
 
<math>\geq 200</math> nucleated cells count requirement
 
Auer rods is a hematopathology determination and not easily collected in EDC
 
Extramedullary disease is a clinical/radiographic determination and not easily collected in EDC
 
Flow cytometry data is a hematopathology determination and is not easily collected in EDC
 
Transfusion independency requirements not specifically defined in IWG 2003 and transfusion independency is not mentioned at all in the ELN 2017
 
Presence of rare peripheral blasts may be normal in a regenerative marrow (medical adjudication required)
 
IWG 2003 ANC requirement is written as “more than” but platelet requirement is written as “<math>\geq</math>” for platelet requirement.
 
“Rare peripheral blast” not defined numerically in IWG 2003 and not mentioned in ELN 2017
 
	
The protocol follows IWG 2003 except:
 
 
Requires lower threshold of nucleated cell count of <math>\geq 100</math>
 
Absolute neutrophil count (ANC) <math>\geq 1,000/\mu L</math>
 
Auer rods and extramedullary disease not collected in EDC
 
Patient must be independent of RBC transfusion and platelet transfusion for a minimum of 1 week before each marrow assessment (Sievers et al 2001; Kantarjian et al 2012)
 
 
RECOMMENDATIONS:
 
 
-Medical adjudication - define rule for when cell count is not available, near 100 cells but not 100 cells, only biopsy is available (no aspirate)
 
-Use ANC <math>\geq 1,000/\mu L</math>
 
-Document in SAP auer rods and extramedullary disease is an investigator/hematopathologist assessment (not part of medical adjudication)
 
-Medical adjudication for cases of CR or CR subtype but a RBC or platelet transfusion was recorded within 1 week
 

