**APPENDIX C: PROGRAMMING GUIDELINES**

Table of response AML assessment status and programmable measures in ASTX727-02 study

Response Assessment Status	Programmable Measures*	Data not evaluable or not easy to capture in EDC (defer to hematopathologist and clinical investigator assessment; or sponsor medical adjudication)
CR	
 
• Marrow blasts: <5%
 
• ANC: <math>\geq 1000/\mu\text{L}</math>
 
• Platelets: <math>\geq 100,000/\mu\text{L}</math>
 
• No RBC and/or platelet transfusion within 7 days of BM evaluation
 
• Peripheral blasts <math>\leq 1\%^1</math>
 
	
 
• Auer rods
 
• Extramedullary disease
 
• Minimum 100 nucleated cell count from aspirate
 
• Flow data evaluating blast morphology
 
• Peripheral blasts present at low % (could be due to regeneration)
 
• CR criteria met but transfusion within 7 days of BM evaluation due to a medical situation
 
• Medical adjudication required when BM and CBC data not assessed on the same day
 

CRi  assess independently in all non-CR cases except progressive disease or relapse/recurrence	
 
• Marrow blasts: <5%
 
• ANC: <math>\geq 1000/\mu\text{L}</math> OR Platelets: <math>\geq 100,000/\mu\text{L}</math>
 
• Transfusion: no RBC and/or platelet transfusion within 7 days of BM evaluation
 
• Peripheral blasts <math>\leq 1\%^1</math>
 
	
 
• Auer rods
 
• Extramedullary disease
 
• Minimum 100 nucleated cell count from aspirate
 
• Flow data evaluating blast morphology
 
• Peripheral blasts present at low % (could be due to regeneration)
 
• CRi criteria met but transfusion within 7 days of BM evaluation due to a medical situation
 
• Medical adjudication required when BM and CBC data not assessed on the same day
 

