CRp  assess independently in all non-CR cases except progressive disease or relapse/recurrence	
 
• Marrow blasts: <5%
 
• ANC: <math>\geq 1000/\mu\text{L}</math>
 
• Platelets: any platelet count <100
 
• Transfusion: no RBC transfusions within 7 days of BM evaluation (no platelet recovery needed so this is independent of platelet transfusion status)
 
• Peripheral blasts <math>\leq 1\%^1</math>
 
	
 
• Auer rods
 
• Extramedullary disease
 
• Minimum 100 nucleated cell count from aspirate
 
• Flow data evaluating blast morphology
 
• Peripheral blasts present at low % (could be due to regeneration)
 
• CRp criteria met but transfusion within 7 days of BM evaluation due to a medical situation
 
• Medical adjudication required when BM and CBC data not assessed on the same day
 

CRh	
 
• Marrow blasts: <5%
 
	
 
• Auer rods
 

Response Assessment Status	Programmable Measures*	Data not evaluable or not easy to capture in EDC (defer to hematopathologist and clinical investigator assessment; or sponsor medical adjudication)
assess independently in all non-CR cases except progressive disease or relapse/recurrence	
 
• ANC: <math>\geq 500/\mu\text{L}</math>
 
• Platelets: <math>\geq 50,000/\mu\text{L}</math>
 
• Transfusion: no RBC and/or platelet transfusions within 7 days of BM evaluation
 
• Peripheral blasts <math>\leq 1\%^1</math>
 
	
 
• Extramedullary disease
 
• Minimum 100 nucleated cell count from aspirate
 
• Flow data evaluating blast morphology
 
• Peripheral blasts present at low % (could be due to regeneration)
 
• CRp criteria met but transfusion within 7 days of BM evaluation due to a medical situation
 
• Medical adjudication required when BM and CBC data not assessed on the same day
 

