**2. Peripheral blasts**

- a. If  $\leq 1\%$  and other CR/CR subtype criteria met, can assume part of regenerating marrow process
- b. If  $>1\%$  and other CR/CR subtype criteria met, use at least one follow-up CBC with differentials to confirm CR/CR subtype criteria (blasts should lessen over days and become  $\leq 1\%$ )
3. Transfusions within 1 week of a CR or CR subtype (expecting to be a rare occurrence)
  - a. If CR/CR subtype criteria met and there is a documented RBC or platelet transfusion within 1 week, consider clinical circumstances of the transfusion - reviewing EDC (AEs, medical hx, concomitant procedures) or asking investigator for details (document and file an administrative letter or as appropriate). This will cover the rare circumstance when the subjects are transfused electively for a medical history, AE, or procedure.

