**4. BM/CBC not on same day (priority of evaluation order)**

- a. Evaluate response using BM biopsy and CBC with differential from the same day
- b. If not matched, look for the closest CBC (usually should be  $\pm 1$  week); assess response using the combination of data and use the later of the two dates as first response
- c. If a marrow is done and a CBC  $>1$  week later shows additional count recovery and meets a new response, enter response at date when CBC data shows criteria met (ask sites to enter any interim missing weekly labs)
- d. If two CBCs are done with the same # days from the marrow and show the same response, use the marrow date for response assessment; if one CBC shows a better response use that CBC and use the date of that CBC
- e. If two CBCs are done with the same # days ( $\pm$ ) from the marrow and show the same response, use the marrow date for response assessment; if the later CBC shows a better response use that CBC date; if the earlier CBC shows a better response, use the BM biopsy date
- f. Note: since CBC with differential on a weekly basis may be critical for proper dating of changes in response assessment (e.g., subject with SD and progressing towards a CR), ask sites to add weekly labs even if local labs (pass to DM to query for all missing weekly labs)

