**5. No interim BM and CR is achieved on a later CBC**

- a. If MLFS (morphologic leukemia-free state), can assess a CR or CR subtype based on a later CBC with diff showing count recovery to meet criteria
- b. If CR subtype (includes MLFS), can assess a CR based on a later CBC with diff showing count recovery to meet criteria
- c. If PR (blasts 5-20%) or SD, cannot assess a higher response category based on a later CBC with diff without a BM evaluation

6. Bone Marrow Blasts Percentages

- a. If BM  $\geq 5\%$  is not seen on laboratory values at screening, to be evaluable, there must be evidence in the EDC supporting the AML diagnosis (BM  $\geq 5\%$ ). To rule out the possibility this is a protocol violation (patient does not have a diagnosis of AML), documentation of either 1) any pre-screening maneuvers that reduced blasts (eg hydroxyurea or single dose of cytarabine or mitoxantrone) or 2) the subject has peripheral blasts  $>20\%$  but not marrow blasts  $>20\%$ , or 3) the subject presents as a myeloid sarcoma which is a type of AML that grows as a tumor and may have a marrow that does not reach AML blast count or is even completely normal. If there is a bone marrow before the screening marrow that documents the AML before #1, ask the site to add the data as an unscheduled BM and date it accordingly for proper documentation and verification of the AML diagnosis. These are the typical circumstances when subjects with AML have blasts  $<20\%$  at baseline.
- b. BM blasts fall from above to below 5% then return above and below 5% again. This may be due to BM rejuvenation. Requires medical adjudication to determine if still in best response or relapsing. Answer to this should be apparent over time.

**APPENDIX E: STANDARD BDM TABLE OUTPUTS OF RESPONSE ASSESSMENT**(1) using 2003 IWG and [Kantarjian et al 2017](#)

Taking ASTX727-02 AML as a sample:

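### The transfusion-free week for AML response is counted from the marrow, but a later blood count can set the response, and the SAP does not say which date governs

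*SAP*

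**What the plan says.** SAP 8.1, Appendix C lists the programmable measures. CR requires "No RBC and/or platelet transfusion within 7 days of BM evaluation". CRi, CRh and PR carry the same condition, worded for CRh as "Transfusion: no RBC and/or platelet transfusions within 7 days of BM evaluation". CRp checks red-cell transfusions only, because there is "no platelet recovery needed so this is independent of platelet transfusion status". The criteria comparison table at the start of SAP 8.1 uses the same reference date: at least one transfusion-free week "before each marrow assessment".

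Two other places word the criterion differently. Table 2 in SAP 7.5.1 asks for independence in the preceding week and names no reference date. Appendix D rule 3 speaks of the week of the CR or CR subtype, and asks the adjudicator to "consider clinical circumstances of the transfusion".

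Appendix D also lets the deciding count come well after the marrow:

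- Rule 4c covers a count more than a week later. If it "shows additional count recovery and meets a new response, enter response at date when CBC data shows criteria met".
- Rule 5a lets a morphologic leukemia-free state become CR or a CR subtype on a later count.
- Rule 5b says that for a subject already in a CR subtype one "can assess a CR based on a later CBC with diff showing count recovery to meet criteria".
- Rule 5c bars any upgrade from PR or stable disease without a new marrow.

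Rules 4c, 5a and 5b set no upper time limit and do not mention transfusions.

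**The concern.** The transfusion condition has a purpose only if it protects the count that decides the response. The CRp exemption shows that the SAP reasons this way: platelet transfusions are ignored exactly where no platelet recovery is needed. By implication, a category with a platelet threshold should rest on the subject's own platelets. If the check looks at the week around the marrow and the deciding count comes weeks later, the program examines the wrong week.

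The misclassification reaches CR, the CR+CRh composite, time to CR, and the durations of CR and of CR or CRh. The study is open-label, and the sponsor's medical monitors evaluate response with the help of programmed listings (SAP 7.5.1), so the rule should be unambiguous before they apply it.

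**Working it through.** The plan gives no figure to reproduce here. The check sets the rules against each other on dates.

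**1. Does the marrow window cover the week before the count?** Put the marrow on Day 0 and the qualifying blood count on Day d. The week before the count is Days d−7 to d−1.

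- If the marrow window means seven days either side, inclusive, it spans Days −7 to 7. For d ≥ 8 the overlap is max(0, 15 − d) days. At d = 8 that is 7 of 7, fully covered. At d = 14 it is 1 of 7 (Day 7 only). From d = 15 it is 0.
- If the window means only the week before the marrow, it spans Days −7 to −1. For d ≥ 8 the week before the count starts on Day 1 or later, so the overlap is 0.
- Rule 4b also allows the nearest count, usually within a week either side. For a count on Day −7 the preceding week is Days −14 to −8, outside both readings.

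**2. Hypothetical subjects** (marrow on Day 0, marrow blasts below 5%, no peripheral blasts, two-sided window). The marrow-dated rule flags a transfusion if it is within 7 days of Day 0. The count-dated rule flags it if it falls in the 7 days before the count.

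| Case | Transfusion | Count | ANC / platelets per µL | Marrow-dated rule | Count-dated rule |
|---|---|---|---|---|---|
| A | Platelets, Day 20 | Day 21 | 1,200 / 105,000 | 20 > 7: passes as CR | 21 − 20 = 1: flagged |
| B | Platelets, Day 20 | Day 21 | 700 / 55,000 | 20 > 7: passes as CRh | 1: flagged |
| C | Platelets, Day 5 | Day 6 | 1,200 / 105,000 | 5 ≤ 7: flagged | 6 − 5 = 1: flagged |
| D | Day −3 | Day 28 | meets CR thresholds | 3 ≤ 7: fails | 28 + 3 = 31: passes |

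Cases A and B err upward and case D errs downward.

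**3. How long is the unprotected stretch?** The supplied protocol (Table 9, bone marrow footnote) has marrows at Day 1 of Cycles 3, 5 and 7, which is 2 × 28 = 56 days apart. With two-sided windows, Days 8 to 48 lie outside both marrows' windows: 48 − 8 + 1 = 41 days. For three-monthly marrows taken as 84 days apart, the stretch is Days 8 to 76: 76 − 8 + 1 = 69 days. If the window is pre-marrow only, the gap opens the day after the marrow.

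**4. Scale.** SAP 4.0 plans about 70 evaluable and 85 randomized subjects. One reclassified subject is 1/70 = 1.4 points or 1/85 = 1.2 points; three are 3/70 = 4.3 or 3/85 = 3.5. As an illustration with an assumed CR rate of 20%, 17/85 = 20.0% (95% Clopper-Pearson 12.1 to 30.1). Removing three gives 14/85 = 16.5% (9.3 to 26.1).

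**The case against.** The strongest reply is that passing the program is not the same as being reported as a response. Every problem case has the marrow and the count on different days, and Appendix C sends all such cases to medical adjudication. Rule 3 can fairly be read as tied to the response date. Rule 4c dates the response at the count, so a transfusion the day before would fall under rule 3. Table 2 is naturally read as the week before the assessment.

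Much of this stands. A reader might infer that the SAP will count transfusion-supported platelets as CR. The documents do not support that, because these cases should reach a reviewer. What the reply does not supply is a rule for that reviewer. Rules 4 and 5, which govern different-day cases, contain no transfusion condition. Through footnote 3, Appendix C refers to Appendix D the case of a transfusion within seven days of the marrow, so rule 3 can equally be read as the exception to the marrow-dated check. On either reading it asks only that circumstances be considered and never says that the response is lost.

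Three further inferences go too far:

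- **That all errors inflate response.** Case D shows a downward error.
- **That PR is exposed in the same way.** Rule 5c closes the late-count route.
- **That rule 3 waivers should be forbidden for platelet transfusions.** The rule is confined to rare, elective transfusions with documentation. Showing its effect is enough.

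**Conclusion.** The SAP dates one criterion in different ways and does not say which date applies when a later count sets the response. As programmed, a transfusion-supported platelet count can pass as CR or CRh, and an unsupported later count can fail because of a transfusion near the marrow. Two careful adjudicators could classify the same subject differently.

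The exposure is mainly CR, CR+CRh, CRh with ANC of 500 to 999/µL, and time to and duration of CR. CR+CRi is less affected, because a platelet-transfused subject with adequate neutrophils can still be CRp, which is listed under CRi. Response is secondary and descriptive (SAP 7.5), and the primary AUC comparison is untouched.

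The size is 1.2 to 1.4 points per reclassified subject. The number of such subjects cannot be derived from the documents, and rule 3 itself expects transfusions close to a response to be rare. The length of the gap assumes that the marrow schedule in the supplied MDS/CMML protocol also holds for AML, since the European and Canadian amendments covering AML were not available. The 20% CR rate is illustrative.

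**What to change.** In Appendix C, for CR, CRi and CRh, count the transfusion-free window as the 7 days before the blood count used for ANC and platelets. For CRp, apply it to red-cell transfusions only. State the same condition in Appendix D rules 4b to 4e, 5a and 5b. Bring Table 2, the criteria comparison table and rule 3 to the same date, and program the flag on it. PR needs no late-count provision.

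Do not add a second window before the marrow for these categories. It would deny CR to a subject such as case D, whose qualifying count is free of transfusion support.

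Report response rates with and without rule 3 waivers as a sensitivity analysis.

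The cost is one programming condition on transfusion dates already collected, plus one extra table. A few responses may change category, in either direction.

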- Bone marrow aspirate or biopsy: At Screening or within 21 days before Cycle 1 Day 1; on or before Day 1 of Cycles 3, 5, 7, and then every 3 months in first year and every 6 months thereafter. Bone marrow aspirate or biopsy differential will be performed according to local standard practice. A bone marrow biopsy can be done if no aspirate is available. A manual differential of the myeloid cells in bone marrow will be performed with a minimum of 100 cells counted and a specific myeloblast percent generated. Bone marrow aspirate or biopsy differential may include the following: total cells counted, metamyelocytes, lymphocytes, normoblasts, myeloid and erythroid maturation, blasts, segmented neutrophils, plasma cells, megakaryocytes, presence of dysplasia, promyelocytes, eosinophils, monocytes, M:E ratio, cellularity: % cellularity; hypocellular, hypercellular, normocellular; myelocytes, basophils, pronormoblasts, and other. An anonymized report of all bone marrow testing results will be recorded on the electronic Case Report Form. A portion of bone marrow aspirates will be used for assessing disease-associated gene mutations. Cytogenetics will be reviewed on the screening bone marrow and should include at least 20 clones. If cytogenetics are abnormal, they must be reviewed again in subsequent bone marrow aspirates or biopsies.

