### 7.5.3 Duration of Response

A combined duration of CR and CRh (in number of days) will be calculated from the first time a CR or CRh is observed to the date of the earliest of the following 3 events: (1) relapse (defined as the earliest time point whereby BM assessment or PB assessment by the investigator indicate relapse/disease progression due to confirmed reappearance of leukemic blasts in PB or  $\geq 5\%$  leukemic blasts in BM, or clinical progression determined by the investigator), (2) start of alternative therapy (except hematopoietic cell transplantation [HCT]) or (3) death. In the absence of any event, the combined duration of CR and CRh will be censored at the last available time point (BM assessment, PB assessment, or safety/long-term follow-up visit) at which an event was not observed. Duration of combined CR and CRh will be analyzed using the Kaplan-Meier method for subjects who achieved a CR or CRh during the study; the median and quartiles of the duration, as well as their respective 95% CIs will be provided. Duration of CR or CRp and duration of CR will be calculated and analyzed similarly.

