Recurrence (IWG 2003) or Relapse (ELN 2017)	
Morphologic relapse after attaining CR.
 
Reappearance of leukemic blasts in the peripheral blood or <math>\geq 5\%</math> blasts in the marrow not attributable to any other cause.
 
Appearance of new dysplastic changes should
	
 
Hematologic relapse (after CRMDR-, CR, CRi) defined as bone marrow blasts <math>\geq 5\%</math>; or reappearance of blasts in the blood; or development of extramedullary disease
 
Molecular relapse (after CRMDR-) defined as if studied pretreatment, reoccurrence of MRD as assessed by RT-qPCR or by MFC
 
	
 
Recurrent or relapse is not easily collected in EDC because it may require the incorporation of marrow and peripheral blood findings, and hematopathology and clinical determination
 
	
 
In SAP, relapse defined as the earliest time point whereby BM assessment or PB assessment by the investigator indicate relapse/disease progression due to confirmed reappearance of leukemic blasts in PB or <math>\geq 5\%</math> leukemic blasts in BM, or clinical progression determined by the investigator
 

AML Response Assessment	IWG 2003 AML Response Criteria 	ELN 2017 AML Response Criteria 	Issues Requiring Clarification(s)	Study-specific Modification(s): ASTX727-02
	also be considered relapse. In the setting of recent treatment, if there are no circulating blasts and the bone marrow blasts are 5-20%, a repeat marrow performed at least a week later is necessary to distinguish relapse from bone marrow regeneration. If recurrence is confirmed, the date of recurrence is defined as the first date that more than 5% blasts were observed in the marrow. Reappearance of extramedullary disease and molecular and/or genetic relapse is characterized by reappearance of the respective abnormalities.			
 
• Auer rods and extramedullary disease not collected in EDC
 
• Appearance of new dysplastic changes are not assessed well (hematopathologist assessment) or collected in EDC
 
• Repeat marrow requirement in case of 5-20% blasts is not necessarily done as part of SOC
 

Footnotes:

 [Cheson et al 2003](#) (IWG):

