Response Assessment Status	Programmable Measures*	Data not evaluable or not easy to capture in EDC (defer to hematopathologist and clinical investigator assessment; or sponsor medical adjudication)
	
 
• Regardless of ANC, platelets, transfusions
 
	
NR not a published criteria	
 
• Response: defined as absence of CR, CRi CRp, CRh, PR (when SD and PD are not assessed)
 
	
 
• Used in place of SD/PD as needed
 

Recurrence (IWG 2003) or Relapse (ELN 2017)	
 
• Response: CR or CR subtype achieved
 
• Marrow blasts: <math>\geq 5\%</math> marrow blasts not attributable to any other cause after CR achieved and sustained on repeat assessment (to distinguish relapse from regeneration)
 
	
 
• Auer rods
 
• Extramedullary disease
 
• Minimum 100 nucleated cell count from aspirate
 
• Frank dysplasia not collected in EDC
 
• Marrow blasts <math>\geq 5\%</math> not attributable to any other cause
 
• Medical adjudication required when BM and CBC data not assessed on the same day
 
• Clinical or symptomatic progression (or incomplete data) accepted for recurrence or relapse assessment
 

The threshold for the purpose of programming was not defined in IWG 2003 and not mentioned in ELN 2017. Requires medical adjudication if present but for programming chose  $\leq 1\%$ .

Data not collected. SAP should state that this data is presumed evaluated/assessed by hematopathologist and clinical investigator as routine part of assessment.

Refer to [Appendix D](#) for guidelines for medical adjudication.

The ELN 2017 criteria mentions “without at least a 100% improvement” in ANC or platelet count - this is difficult to capture in the EDC or evaluate by programming. Omitted this detail in the table since AML is not an indolent disease and progressive disease tends to be obvious with other supportive laboratory and clinical data.

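### The SAP's two AML relapse definitions do not match: Section 7.5.3 counts blasts reappearing in blood, but the Appendix C programmable measure counts only a repeated marrow finding

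*SAP*

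**What the plan says.** **SAP Section 7.5.3 (Duration of Response).** Relapse is "defined as the earliest time point whereby BM assessment or PB assessment by the investigator indicate relapse/disease progression". The laboratory routes are "due to confirmed reappearance of leukemic blasts in PB" or at least 5% leukemic blasts in marrow. Clinical progression as judged by the investigator is a third route. Alternative therapy (other than transplantation) and death also end the duration. With no event, the duration "will be censored at the last available time point", which may be a marrow, a blood assessment or a follow-up visit.

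**SAP Section 8.1, criteria table, recurrence/relapse row.** The study-specific column restates the Section 7.5.3 definition, blood route included. It also notes: "Repeat marrow requirement in case of 5-20% blasts is not necessarily done as part of SOC". In the same row, the IWG 2003 and ELN 2017 columns both count return of blasts in blood. The IWG column asks for a repeat marrow only after recent treatment, with no circulating blasts and marrow blasts of 5-20%. It dates a confirmed recurrence back to the first marrow above 5%.

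**SAP Section 8.1, Appendix C, relapse row.** After CR or a CR subtype, the only programmable finding is at least 5% "marrow blasts not attributable to any other cause after CR achieved and sustained on repeat assessment". A further column, for matters left to the hematopathologist, the investigator or sponsor adjudication, accepts clinical or symptomatic progression or incomplete data.

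**SAP Section 7.5.1.** Sponsor medical monitors evaluate response, assisted by programmed listings.

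**The concern.** Relapse ends duration of CR, of CR or CRp, and of combined CR and CRh (Section 7.5.3). It is also an event in EFS (Section 7.5.7) and PFS (Section 7.5.8), neither of which defines it. A programmer working from Appendix C and a statistician working from Section 7.5.3 would flag different subjects.

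The missing blood criterion is not a data limitation. Appendix C programs a peripheral-blast ceiling of 1% for CR, CRi, CRp, CRh and PR, so blood blasts help to award a response but do not help to end it. Any error would run one way, towards longer durations.

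**Working it through.** The plan states no figure on this point, so the check sets the passages side by side and then sizes the possible date shift by illustration.

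**1. The definitions**

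| Element | Section 7.5.3 and criteria table | Appendix C programmable measure |
|---|---|---|
| Blood blasts | Count, if confirmed | Absent |
| Marrow blasts at least 5% | Count; unclear whether the word confirmed extends to marrow | Count only if sustained on repeat |
| Investigator-determined progression | Counts | Not programmed; accepted in the deferral column |
| Date | Earliest time point | No rule |
| No repeat marrow | Not addressed | Measure not met; deferral column accepts incomplete data |

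**2. Whether adjudication closes the gap.** Appendix D rule 2 uses blood blasts only to confirm CR or a CR subtype. Rule 6b sends marrow blasts that move back and forth across 5% to adjudication and gives no date. The Appendix C progression row has a blood route, but it needs a rise of more than 50% to at least 25 × 10⁹/L. No rule tells a monitor to call relapse on blood blasts.

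**3. Two test cases**
- *A subject in CR with 8% blood blasts on two successive counts and no marrow.* This is relapse under Section 7.5.3 if a second count is confirmation. The Appendix C measure is not met.
- *A subject in CR with one marrow at 12% and no repeat.* This is relapse under Section 7.5.3 unless confirmation also applies to marrow. The Appendix C measure is not met, but the incomplete-data allowance could cover it. The status is unsettled.

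**4. What happens to an unflagged relapse**

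| Endpoint | Other events that end it | Otherwise censored at |
|---|---|---|
| Duration of response | Alternative therapy (not transplantation), death | Last available time point |
| EFS | Discontinuation for progression or a treatment-related adverse event, alternative therapy (not transplantation), death | Last known alive |
| PFS | Death (alternative therapy is not an event) | Last known alive |

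**5. Illustration of the date shift.** Inputs from Protocol Table 9: marrow at Cycles 3, 5 and 7 (28-day cycles, so g = 56 days), then "every 3 months in first year and every 6 months thereafter" (g about 91 and 182 days); blood counts on Days 1 and 15 from Cycle 3 (about every 14 days). Assumptions: this schedule applies to the AML cohort, whose protocol amendment is not supplied; every relapse shows in both blood and marrow; time to relapse is exponential with median 180, 270 or 365 days.

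If relapse falls evenly within a marrow interval, the mean delay of marrow dating against first-positive-blood dating is about g/2 − 14/2:
- g = 56: 28 − 7 = 21 days
- g = 91: 45.5 − 7 = 38.5 days
- g = 182: 91 − 7 = 84 days

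Simulation under the exponential assumption gave these mean delays in days:

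| Relapse dated at | g = 56 | g = 91 | g = 182 |
|---|---|---|---|
| First marrow at least 5% | 21-22 | 40-41 | 89-94 |
| Repeat marrow 7 days later | 28-29 | 47-48 | 96-101 |
| Next scheduled marrow | 77-78 | 131-132 | 271-276 |

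With back-dating to the first positive marrow, as in the IWG text, only the first row applies. The repeat then adds no delay. All values are upper-end, because every relapse was assumed visible in blood.

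**The case against.** The strongest reply is that the Appendix C measure is not the final word. Medical monitors decide, listings only assist them, and Section 7.5.3 makes relapse an investigator-indicated event. The relapse row also accepts clinical progression or incomplete data. On this view the mismatch affects a programmed flag and need not affect the adjudicated endpoint. That stands as a limit on the claim. It does not remove the conflict, because Section 8.1 is meant to be detailed enough for programming and its adjudication rules are silent on relapse in blood.

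A reader might infer that relapses without a second marrow are lost, or that they are dated three to six months late. The documents support neither. The incomplete-data allowance can cover a missing repeat. Appendix C has no dating rule, and requiring confirmation is not the same as dating at confirmation; the only dating text for a confirmed marrow recurrence works backwards to the first positive marrow. The contrast on marrow is also softer than it looks, since the word confirmed in Section 7.5.3 can be read to cover both laboratory routes.

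A reader might also take the 1% blood ceiling as a ready-made relapse threshold. It governs the award of a response only, and Appendix D rule 2 allows for values above 1% that fall on follow-up.

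Finally, alternative therapy or death ends duration of response and EFS in many subjects whose relapse went unflagged. That is a real limit for those endpoints. PFS has no alternative-therapy event.

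**Conclusion.** The conflict is real and should be resolved. Its clearest part is the blood criterion, which is present in Section 7.5.3 and the criteria table and absent from the Appendix C measure. The repeat-marrow requirement is a second mismatch, and the SAP itself says that the repeat may not be done.

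If the programmed flag drives the analysis, a relapse first seen in blood can be missed or dated later. That would lengthen duration of CR, of CR or CRp and of combined CR and CRh, as well as PFS and EFS. The documents do not establish the size. The illustrative delays rest on an assumed schedule, assumed relapse times and universal visibility in blood, so they show scale only.

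Section 7.5 makes these analyses descriptive, with no formal comparison between sequences, and the primary AUC analysis is untouched. The change is one the plan should make, but nothing in the primary conclusion depends on it.

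**What to change.** Make the Appendix C relapse row match Section 7.5.3 and the criteria table:

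- Add confirmed return of blasts in blood, and investigator-determined progression, as relapse routes beside the marrow route.
- Date relapse at the first abnormal finding. This agrees with the earliest-time-point wording of Section 7.5.3 and with the IWG back-dating already quoted in the criteria table.
- State what confirmation requires: any blood-blast cut-off, and whether confirmation applies to marrow as well as blood. The documents give no relapse cut-off for blood, so one must be chosen and stated.
- State that a single marrow of at least 5% with no repeat goes to adjudication and is not treated as no relapse.

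The cost is SAP wording and derivation code on marrow and hematology data already collected. Some reported durations may become shorter, and a few cases of marrow regeneration will need adjudication.
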